during the screening process or between visits, or through physical examination, laboratory test, or other assessments. As far as possible, each adverse event should be evaluated to determine:

1. The severity grade (CTCAE Grade 1-5)
2. Its duration (Start and end dates)
3. Its relationship to the study treatment (Reasonable possibility that AE is related: No, Yes)
Action taken with respect to study or investigational treatment (none, dose adjusted, temporarily interrupted, permanently discontinued, unknown, not applicable)
4. Whether medication or therapy was given (no concomitant medication/non-drug therapy, concomitant medication/non-drug therapy)
5. Whether it is serious, where a serious adverse event (SAE) is defined as in [Section 8.2.1](#) and which seriousness criteria have been met

If the event worsens the event should be reported a second time in the CRF noting the start date when the event worsens in toxicity. For grade 3 and 4 adverse events only, if improvement to a lower grade is determined a new entry for this event should be reported in the CRF noting the start date when the event improved from having been Grade 3 or Grade 4.

All adverse events should be treated appropriately. If a concomitant medication or non-drug therapy is given, this action should be recorded on the Adverse Event CRF.

Once an adverse event is detected, it should be followed until its resolution or until it is judged to be permanent, and assessment should be made at each visit (or more frequently, if necessary) of any changes in severity, the suspected relationship to the study treatment, the interventions required to treat it, and the outcome.

Progression of malignancy (including fatal outcomes), if documented by use of appropriate method (for example, as per RECIST criteria for solid tumors), should not be reported as a serious adverse event.

Adverse events separate from the progression of malignancy (example, deep vein thrombosis at the time of progression or hemoptysis concurrent with finding of disease progression) will be reported as per usual guidelines used for such events with proper attribution regarding relatedness to the drug.

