10.5.3.2 Adverse events (AEs)

Summary tables for adverse events (AEs) will include only AEs that started or worsened during the on-treatment period, the **treatment-emergent** AEs. Additional summaries will be displayed to report deaths, all AEs, AEs related to study treatment, all SAEs and SAEs related to study treatment collected up to **150** days after last administration of PDR001.

The incidence of treatment-emergent adverse events (new or worsening from baseline) will be summarized by system organ class and or preferred term, severity (based on CTCAE grades), type of adverse event, relation to study treatment.

Serious adverse events, non-serious adverse events and adverse events of special interest (AESI) during the on-treatment period will be tabulated.

All deaths (on-treatment and post-treatment) will be summarized.

All AEs, deaths and serious adverse events (including those from the pre and post-treatment periods) will be listed and those starting during the post-treatment period will be flagged.

Project-specific AESIs should be defined in the case retrieval strategy (CRS) with regular updates whenever necessary, see also [Section 8.1.3](#).

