For safety and efficacy evaluations, the last available assessment on or before the date of start of study treatment is defined as “baseline” assessment.

If patients have no value as defined above, the baseline result will be missing.

On-treatment assessment/event and observation periods

For adverse event reporting the overall observation period will be divided into three mutually exclusive segments:

1. ***pre-treatment period***: from day of patient’s informed consent to the day before first administration of study treatment
2. ***on-treatment period***: from date of first administration of study treatment to 30 days after date of last actual administration of any study treatment (including start and stop date)
3. ***post-treatment period***: starting at day 31 after last administration of study treatment.

Safety summaries (tables, figures) include only data from the on-treatment period with the exception of baseline data which will also be summarized where appropriate (e.g. change from baseline summaries). In addition, a separate summary for death including on treatment and post treatment deaths will be provided. In particular, summary tables for adverse events (AEs) will summarize only on-treatment events, with a start date during the on-treatment period (***treatment-emergent*** AEs).

Additional summaries will be displayed to report deaths, all AEs, AEs related to study treatment, all SAEs and SAEs related to study treatment collected up to 150 days after last administration of PDR001.

However, all safety data (including those from the post-treatment period) will be listed and those collected during the pre-treatment and post-treatment period will be flagged.

Last contact date

The last contact date will be derived for patients not known to have died at the analysis cut-off using the last complete date among the following:

Table 2-1 Last contact date data sources

Source data	Conditions
Last contact date/last date patient was known to be alive from Survival Follow-up page	- Patient status is reported to be alive, lost to follow-up or unknown.
Start/End dates from further antineoplastic therapy	Non-missing medication/procedure term.
Start/End* dates from drug administration record	Non-missing dose. Doses of 0 are allowed.
End of treatment date from end of treatment page	No condition.
Tumor (RECIST/irRECIST) assessment date	Evaluation is marked as 'done'.

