2.8.1 Adverse events (AEs)

AE summaries will include all AEs occurring during on treatment period. Additional summaries will be displayed to report all AEs, AEs related to study treatment, all SAEs and SAEs related to study treatment collected up to 150 days after last administration of PDR001. All AEs collected in the AE (e)CRF page will be listed along with the information collected on those AEs e.g. AE relationship to study drug, AE outcome etc. AEs with start date outside of on-treatment period will be flagged in the listings.

AEs will be summarized by number and percentage of subjects having at least one AE, having at least one AE in each primary system organ class (SOC) and for each preferred term (PT) using MedDRA coding. A subject with multiple occurrences of an AE will be counted only once in the respective AE category. A subject with multiple CTCAE grades for the same preferred term will be summarized under the maximum CTCAE grade recorded for the event. AE with missing CTCAE grade will be included in the 'All grades' column of the summary tables.

In AE summaries, the primary system organ class will be presented alphabetically and the preferred terms will be sorted within primary SOC in descending frequency. The sort order for the preferred term will be based on their frequency in the investigational arm.

The following adverse event summaries will be produced using the safety set; overview of adverse events and deaths, AEs by SOC and PT, summarized by relationship, seriousness, leading to treatment discontinuation, leading to dose interruption/adjustment, requiring additional therapy, requiring immunosuppressive medication and leading to fatal outcome. In

addition, a summary of serious adverse events with number of occurrences will be produced (an occurrence is defined as >1 day between start and prior end date of record of same preferred term).

For the legal requirements of ClinicalTrials.gov and EudraCT, two required tables on on-treatment adverse events which are not serious adverse events with an incidence greater than 5% and on on-treatment serious adverse events and SAE suspected to be related to study treatment will be provided by system organ class and preferred term on the safety set population.

If for a same patient, several consecutive AEs (irrespective of study treatment causality, seriousness and severity) occurred with the same SOC and PT:

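### The SAP's start-date rule for treatment-emergent AEs drops the protocol's worsening condition, so some screening grade 3/4 events that improve on treatment would be tabulated as treatment-emergent

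*Protocol*

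**What the plan says.** Protocol 8.1.1 collects AEs from informed consent and splits a changing event into several CRF entries. On worsening: "If the event worsens the event should be reported a second time in the CRF noting the start date when the event worsens in toxicity". Grade 3 and 4 events have a second trigger: "if improvement to a lower grade is determined a new entry for this event should be reported in the CRF noting the start date" of that improvement.

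Protocol 10.5.3.2 says that the AE summary tables "will include only AEs that started or worsened during the on-treatment period". Its next paragraph says that treatment-emergent "adverse events (new or worsening from baseline) will be summarized by system organ class", among other groupings.

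SAP 2.1.1 has a pre-treatment period that runs from the day of "informed consent to the day before first administration of study treatment". It then states that "summary tables for adverse events (AEs) will summarize only on-treatment events, with a start date during the on-treatment period", and these are its treatment-emergent AEs. SAP 2.8.1 repeats the scope: "AE summaries will include all AEs occurring during on treatment period". In the listings it flags AEs by start date. Neither SAP section compares an entry with the grade before treatment.

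SAP section 4 declares one departure from the protocol's analyses, which is dropping the evaluation of heterogeneity between the three cohorts. It says that there is no other.

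**The concern.** A start-date filter can stand in for the protocol's condition only if new entries arise at onset or at worsening and at no other time. The improvement entry breaks that. It carries an on-treatment start date although the event began before the first dose and then got better. The SAP would tabulate it; the protocol's definition would not.

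What is at stake is the all-causality incidence of treatment-emergent AEs in a single-arm trial, where no control rate would carry the same error. For these records the error runs one way, upwards, and the denominators are small.

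**Working it through.** The plan states no figure to reproduce here. The check traces record sequences through both rules and then weighs one patient.

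**Inputs**
- Entry rules on worsening and improvement: protocol 8.1.1.
- Conditions present at consent go to Medical History, not to the AE pages: protocol 8.1.1.
- Screening lasts at most 28 days: protocol 7.1.2.
- On-treatment period, from first dose to 30 days after last dose: SAP 2.1.1.
- Each patient counts once per AE category, at the maximum grade for the preferred term: SAP 2.8.1.
- Treated patients, 95 well-differentiated and 21 GEP-NEC: protocol 1.2.1.2. The safety set is defined in the same way as the FAS, and Amendment 3 closes enrolment.

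**Rules**
- SAP: a record counts if first dose ≤ start date ≤ last dose + 30 days.
- Protocol: as above, and the grade must exceed the pre-treatment grade of the same event (0 if there was none).

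| Sequence | SAP rule | Protocol rule |
|---|---|---|
| Screening grade 3, falls to 1 on treatment | counted, grade 1 | not counted |
| Screening grade 4, falls to 3 on treatment | counted, grade 3 | not counted |
| Screening grade 3, unchanged | not counted | not counted |
| Screening grade 2, falls to 1 (no new entry required) | not counted | not counted |
| Onset on treatment at grade 3, falls to 1 | once, grade 3 | once, grade 3 |
| Screening grade 1, rises to 3 on treatment | counted, grade 3 | counted, grade 3 |

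The rules part only in the first two rows. The last row shows that true worsening is already caught, because 8.1.1 gives it its own dated entry.

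**Does another SAP rule repair this?** SAP 2.8.1 merges consecutive records of the same preferred term when the gap is at most 1 day, but it does so for occurrence counts. It does not say whether the merging comes before or after the on-treatment filter, and it does not exclude a block that began before the first dose. Neither document ties an improvement entry to its parent event.

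**Weight of one patient not already counted for the term**
- Well-differentiated: 1/95 = 1.05 points.
- GEP-NEC: 1/21 = 4.76 points.
- Pooled: 1/116 = 0.86 points.

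**Registry table.** SAP 2.8.1 plans a table of non-serious AEs above 5% incidence. The smallest counts over that line are 5/95 (5.26%), 2/21 (9.52%) and 6/116 (5.17%). If the threshold is applied within GEP-NEC, one extra patient moves a term from 1/21 (4.76%) to 2/21 (9.52%) and so into the table.

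**The case against.** Four arguments stand against the point.

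**The protocol already has the right definition.** The SAP is based on that protocol and declares no relevant change, so the two could be read together. Protocol 8.1.1 also treats the improvement record as part of the same event, whose onset was before treatment. This shows that the SAP wording is open to a better reading. It does not settle the matter, because the SAP states its own operative rule, a start date, and SAP 2.8.1 itself refers to consecutive records as AEs. A programmer who follows the SAP would filter records by date.

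**The affected set is narrow.** This stands in full. The event must begin, or reach grade 3 or 4, between consent and first dose, and then improve after dosing to a lower grade without resolving. The patient must have no other on-treatment record of that term. Exclusions 15, 19 and 21 and the laboratory limits in inclusion 12 also keep some patients with severe screening events from being dosed.

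**It is not drug toxicity.** A reader might infer that improving pre-treatment events would be reported as toxicity of PDR001. The documents do not support that. The investigator records relationship as yes or no for each AE, and related AEs have their own tables. Treatment-emergent describes timing and does not attribute cause. An effect on SAE tables would likewise require the improved entry still to be marked serious.

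**The consequence is mild.** Safety tables are descriptive, the error overstates AEs, and the pre-treatment parent record stays visible and flagged in the listings. This too stands, and it bears on severity.

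**Conclusion.** The mismatch is real and undeclared: SAP 2.1.1 and 2.8.1 leave out the worsening condition of protocol 10.5.3.2, and the CRF's improvement entries make that omission matter. Read literally, the SAP tabulates certain improving screening events that the protocol excludes, at their lower on-treatment grade and in all-causality rows. Related-AE rows change only if the entry is marked related. Grade 3 rows change only after a fall from grade 4 to 3.

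The size per patient is 1.1 points in the well-differentiated group and 4.8 points in GEP-NEC, provided that the patient is not already counted for the term. The documents do not give the number of such patients; given the conditions above it is probably small and may be zero. The conclusion assumes that the tables are programmed from record start dates as SAP 2.1.1 is worded. Severity: minor.

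**What to change.** In SAP 2.1.1 and 2.8.1, define a treatment-emergent AE as one that is new on treatment, or whose grade on treatment exceeds the highest pre-treatment grade of the same continuing event. Before the on-treatment filter is applied, link consecutive records of the same preferred term with a gap of at most 1 day to the original onset date. Keep the excluded continuation records in the listings with a flag.

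Two details matter:
- The reference should be the pre-treatment grade, not the preceding record. With screening grade 3, then grade 1 and then grade 2 on treatment, the last record is above its predecessor but below the pre-treatment grade. A record-to-record comparison would still count it.
- Linking must come with the grade condition. If records were only moved back to their original onset date, screening events that truly worsen on treatment would be lost.

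The cost is a short SAP edit and one programming step. Preferred term, dates and grade are already collected, so no new data are needed.

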8.1.2 Laboratory test abnormalities

8.1.2.1 Definitions and reporting

Laboratory abnormalities that constitute an Adverse event in their own right (are considered clinically significant, induce clinical signs or symptoms, require concomitant therapy or require changes in study treatment), should be recorded on the Adverse Events CRF. Whenever possible, a diagnosis, rather than a symptom should be provided (e.g. anemia instead of low hemoglobin). Laboratory abnormalities that meet the criteria for Adverse Events should be followed until they have returned to normal or an adequate explanation of the abnormality is found. When an abnormal laboratory or test result corresponds to a sign/symptom of an already reported adverse event, it is not necessary to separately record the lab/test result as an additional event.

Laboratory abnormalities, that do not meet the definition of an adverse event, should not be reported as adverse events. A Grade 3 or 4 event (severe) as per CTCAE does not automatically indicate a SAE unless it meets the definition of serious as defined below and/or as per investigator's discretion. A dose hold or medication for the lab abnormality may be required by the protocol in which case the lab abnormality would still, by definition, be an adverse event and must be reported as such.

8.1.3 Adverse events of special interest

Adverse events of special interest (AESI) are defined as events (serious or non-serious) which are ones of scientific and medical concern specific to the sponsor's product or program, for which ongoing monitoring and rapid communication by the investigator to the sponsor may be appropriate. Such events may require further investigation in order to characterize and understand them.

Adverse events of special interest are defined on the basis of an ongoing review of the safety data. The following AESIs are discussed in detail in the latest [Investigator Brochure]:

- Endocrinopathies (Hypothyroidism, hyperthyroidism, diabetes, hypophysitis and hypopituitarism)
- Pneumonitis
- Diarrhea/colitis
- Hepatitis
- Nephritis
- Encephalitis
- Skin/rash

8.2 Serious adverse events

8.2.1 Definitions

Serious adverse event (SAE) is defined as one of the following:

- Is fatal or life-threatening
- Results in persistent or significant disability/incapacity
- Constitutes a congenital anomaly/birth defect
- Is medically significant, i.e., defined as an event that jeopardizes the patient or may require medical or surgical intervention to prevent one of the outcomes listed above
- Requires inpatient hospitalization or prolongation of existing hospitalization,
- Note that hospitalizations for the following reasons should not be reported as serious adverse events:
 - Routine treatment or monitoring of the studied indication, not associated with any deterioration in condition
 - Elective or pre-planned treatment for a pre-existing condition that is unrelated to the indication under study and has not worsened since signing the informed consent

- Social reasons and respite care in the absence of any deterioration in the patient's general condition
- Note that treatment on an emergency outpatient basis that does not result in hospital admission and involves an event not fulfilling any of the definitions of a SAE given above is not a serious adverse event

8.2.2 Reporting

To ensure patient safety, every SAE, regardless of suspected causality, occurring after the patient has provided informed consent must be reported to Novartis within 24 hours of learning of its occurrence and until:

- Suspected SAEs up to 150-Day safety follow-up and beyond
- Non-suspected SAEs up to 150-Day safety follow-up or start of new post treatment anti-neoplastic medication if administered during the period between the 30-Day safety follow-up and 150-Day safety follow-up, whichever is sooner (see [Appendix 3](#))

If a patient starts a post treatment antineoplastic therapy after the 30-Day safety follow-up, then only SAEs suspected to be related to study treatment should be collected out to 150 days after discontinuation of PDR001. SAEs suspected to be related to PDR001 will continue to be collected beyond the 150-Day safety follow-up visit.

Any additional information for the SAE including complications, progression of the initial SAE, and recurrent episodes must be reported as follow-up to the original episode within 24 hours of the investigator receiving the follow-up information. An SAE occurring at a different time interval or otherwise considered completely unrelated to a previously reported one should be reported separately as a new event.

Any SAEs experienced after the reporting period described above should only be reported to Novartis if the investigator suspects a causal relationship to the study treatment.

Information about all SAEs is collected and recorded on the Serious Adverse Event Report Form; all applicable sections of the form must be completed in order to provide a clinically thorough report. The investigator must assess and record the relationship of each SAE to each specific study treatment (if there is more than one study treatment), complete the SAE Report Form in English, and submit the completed form within 24 hours to Novartis. Detailed instructions regarding the SAE submission process and requirements for signatures are to be found in the investigator folder provided to each site.

Follow-up information is submitted in the same way as the original SAE Report. Each re-occurrence, complication, or progression of the original event should be reported as a follow-up to that event regardless of when it occurs. The follow-up information should describe whether the event has resolved or continues, if and how it was treated, whether the blind was broken or not, and whether the patient continued or withdrew from study participation.

If the SAE is not previously documented in the Investigator's Brochure or Package Insert (new occurrence) and is thought to be related to the Novartis study treatment, an oncology Novartis Chief Medical Office and Patient Safety (CMO&PS) department associate may urgently require further information from the investigator for Health Authority reporting. Novartis may need to issue an Investigator Notification (IN), to inform all investigators involved in any study with

the same drug that this SAE has been reported. Suspected Unexpected Serious Adverse Reactions (SUSARs) will be collected and reported to the competent authorities and relevant ethics committees in accordance with Directive 2001/20/EC or as per national regulatory requirements in participating countries.

8.3 Emergency unblinding of treatment assignment

Not applicable

8.4 Pregnancies

To ensure patient safety, each pregnancy occurring while the patient is on study treatment must be reported to Novartis within 24 hours of learning of its occurrence. The pregnancy should be followed up to determine outcome, including spontaneous or voluntary termination, details of the birth, and the presence or absence of any birth defects, congenital abnormalities, or maternal and/or newborn complications.

Pregnancy should be recorded on a Clinical Trial Pregnancy Form and reported by the investigator to the oncology Novartis CMO&PS. Pregnancy follow-up should be recorded on the same form and should include an assessment of the possible relationship to the study treatment any pregnancy outcome. Any SAE experienced during pregnancy must be reported on the SAE Report Form.

Pregnancy outcomes should be collected for the female partners of any males who took study treatment in this study. Consent to report information regarding these pregnancy outcomes should be obtained from the mother.

